### 7.3 LOST TO FOLLOW-UP

A participant will be considered lost to follow-up if he or she fails to return for two scheduled visits and study staff are unable to contact the participant after at least 3 attempts.

The following actions must be taken if a participant fails to return to the clinic for a required study visit:

- The site will attempt to contact the participant, reschedule the missed visit within 2 weeks, counsel the participant on the importance of maintaining the assigned visit schedule and ascertain if the participant wishes to and/or should continue in the study
- Before a participant is deemed lost to follow-up, the investigator or designee will make every effort to regain contact with the participant (where possible, 3 telephone calls and, if necessary, a certified letter to the participant's last known mailing address or local equivalent methods). These contact attempts will be documented in the participant's medical record or study file.
- Should the participant continue to be unreachable, he or she will be considered to have withdrawn from the study with a primary reason of lost to follow-up.

# 8 STUDY ASSESSMENTS AND PROCEDURES

#### 8.1 ENDPOINT AND OTHER NON-SAFETY ASSESSMENTS

#### Primary Endpoint

Initiation of postoperative PORT > 6 weeks after surgery is defined as more than 42 calendar days from the time of the definitive surgical resection to the initiation of radiation therapy. In situations in which the surgical management of the primary tumor and the neck are staged (i.e. occur on two different calendar days), the date of the surgery for the primary tumor will be used. In situations in which an additional surgical resection is required (e.g. re-resection of positive margins to clear residual disease), the date of the earlier (i.e. attempted definitive) surgical procedure will be used to determine the target start date for PORT.

#### Secondary Endpoints Clinical Outcomes

Racial disparities in initiation of PORT > 6 weeks after surgery is defined as the difference in the rate of initiation of PORT > 6 weeks after surgery between white and AA HNC patients.

Days between surgery and the start of PORT is defined as the time, in days, between the date of definitive surgical resection to the initiation of radiation therapy. All of the criteria used to adjudicate the date of the definitive surgical procedure described for the primary outcome measure will be applied to this measure.

Barriers resolved is the number of barriers identified by the navigator that are resolved during the NDURE intervention, as determined by the navigator log.

Unresolved barriers is the number of barriers identified by the navigator that are not resolved during the NDURE intervention, as determined by the navigator log.

Pre-Surgical Radiation Consultation is defined as the attendance by the patient at a consultation with a radiation oncologist (at MUSC or elsewhere) prior to surgery to discuss RT in the definitive or adjuvant setting

Pre-Radiation Therapy Dental Extractions is defined as the extraction of teeth prior to discharge from the index hospitalization for the definitive surgical procedure. Patients who are edentulous are not evaluable for this measure.

Surgery to Pathology Report </= 7 days is defined as the production of the pathology report from the definitive surgical procedure within the EMR within 7 calendar days of the definitive surgical procedure. Addenda to the pathology report at the request of the HNC team (e.g. tumor p16 status) are not counted in this measure.

Surgery to PORT Referral </= 10 days is defined as the placement of a referral for PORT, at MUSC or elsewhere, within 10 calendar days of the definitive surgical procedure.

RT Referral to Consult </= 10 days is defined as the evaluation of the patient at a postoperative consultation with a radiation oncologist within 10 calendar days of the referral being placed (or postoperative appointment being scheduled in cases in which care has been established and the return visit is no longer a consultation). The consultation may occur in the clinic or the hospital depending upon clinical circumstances.

RT Consult to Initiation </= 21 days is defined as the initiation of PORT within 21 calendar days of the patient being evaluated by a radiation oncologist for PORT.

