Secondary endpoints for feasibility, acceptability, fidelity and HNC care delivery will be analyzed as follows. For study accrual, we will calculate the proportion and frequency of eligible patients who accrue (overall, white, and AA). Given its pilot nature, the study is not designed to evaluate racial differences in accrual, although reasons for study decline will be collected, analyzed by race, and used to refine recruitment. NDURE completion will be analyzed as 1) the percentage of enrolled patients who attend all three in-person NDURE sessions and 2) the proportion of three in-person NDURE sessions that are completed. For navigator caseload, we will consider the frequency of simultaneous cases navigated. Navigator time allocation for direct and indirect time, as well as patient-report measures of satisfaction with navigation (acceptability) will be summarized as described above for continuous data. NDURE fidelity will be analyzed as the proportion of enrolled patients who have a BRP documented in the EMR. For HNC care delivery processes, we will calculate the proportion of patients receiving each key HNC care delivery process.

For secondary endpoints evaluating the theoretical constructs underlying NDURE (care coordination, support, perceived susceptibility, severity, barriers, and self-efficacy), we will estimate the mean change in each measure (pre-post) as well as standard deviations and 95% CIs for each; comparisons will be conducted using Wilcoxon sign-rank test. Baseline levels of each dependent variable will be controlled in each model; additional covariates will be considered by examining associations between potential covariates and each dependent variable using linear regression (p < .10 where the change in each outcome measure is the dependent variable). This method will allow estimation of intervention effects while adjusting for potential confounders.

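### The 10-day RT Referral to Consult clock can start before surgery but must stop after it, so early referral or booking tends to be scored as a failure

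*Combined protocol and SAP*

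**What the plan says.** Section 8.1 (Secondary Endpoints, Clinical Outcomes) lists pre-surgical radiation consultation as a care process in its own right: attendance "prior to surgery to discuss RT in the definitive or adjuvant setting". It then defines three intervals:

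- **Surgery to PORT Referral:** "placement of a referral for PORT, at MUSC or elsewhere, within 10 calendar days of the definitive surgical procedure".
- **RT Referral to Consult:** "the evaluation of the patient at a postoperative consultation with a radiation oncologist within 10 calendar days of the referral being placed". For patients with established care the start is replaced by the "postoperative appointment being scheduled in cases in which care has been established and the return visit is no longer a consultation".
- **RT Consult to Initiation:** "the initiation of PORT within 21 calendar days of the patient being evaluated by a radiation oncologist for PORT".

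The primary endpoint in the same section counts PORT as delayed when it starts more than 42 days after surgery. For the care processes, Section 9.4.3 says "we will calculate the proportion of patients receiving each key HNC care delivery process". No section says how a referral or appointment made before surgery enters the second interval.

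**The concern.** The second interval has a start date that may fall on either side of surgery and an end event that may fall only after it. Arranging the postoperative visit earlier therefore lengthens the measured interval without changing when the patient is seen. Arranging it late shortens the interval.

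Such patients are foreseeable. Section 5.1 requires PORT to be judged likely at screening, and Section 6.1.1 has the navigator build and start the barrier reduction plan at the first session, which coincides with the presurgical consult. Section 4.1 lists delivery of key care processes as a secondary outcome, and Section 4.2 says the trial is to inform a larger cluster-randomized trial. A measure that marks early arrangement as a failure would misdescribe delivery here and could carry into that trial.

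**Working it through.** **Inputs.** Limits of 10, 10 and 21 days and the 42-day PORT limit (Section 8.1); n = 45 and a maximum margin of error of 0.15 (Section 9.2). Surgery is day 0. The patient dates are illustrative.

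**1. The plan's own figures.** The three limits sum to 10 + 10 + 21 = 41 days, just inside 42. This suggests that they were meant as consecutive postoperative segments. The plan gives no target rate for these measures. Its margin of error reproduces: 1.96 × √(0.5 × 0.5 / 45) = 0.146, stated as 0.15. It serves below only as a yardstick.

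**2. Condition for passing.** With clock start on day s and the postoperative visit on day v, the measure is met if v − s ≤ 10, that is, v ≤ s + 10. For s = −7 the patient must be seen by day 3. For s = −14 the limit is day −4, which no postoperative visit can meet.

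**3. Day counts.**

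| Patient | Clock start | Seen | PORT | Interval | Scored | PORT timely |
|---|---|---|---|---|---|---|
| A: established, booked before surgery | −7 | 14 | 34 | 14 − (−7) = 21 | not met | yes |
| B: established, booked before surgery | −7 | 18 | 38 | 18 − (−7) = 25 | not met | yes |
| C: not established, referred before surgery | −14 | 18 | 38 | 18 − (−14) = 32 | not met | yes |
| D: established, booked after surgery | 8 | 18 | 38 | 18 − 8 = 10 | met | yes |
| E: established, booked late | 35 | 40 | 60 | 40 − 35 = 5 | met | no |
| F: referred after surgery | 10 | 20 | 41 | 20 − 10 = 10 | met | yes |

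B and D are seen on the same day and start PORT on the same day. Only the booking date differs, and the earlier booking fails.

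**4. The two neighbouring measures.**
- *Surgery to PORT Referral.* A referral on day −14 satisfies a limit of no later than day 10. It fails only if the limit is read as 10 days either side of surgery.
- *RT Consult to Initiation.* Suppose B had a pre-surgical consult on day −10. Counting from the postoperative visit gives 38 − 18 = 20 days (met). Counting from the pre-surgical consult gives 38 − (−10) = 48 days (not met). On that second reading, a consult on day −1 would require PORT by day −1 + 21 = 20.

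**5. Size.** The share of patients affected is not in the documents. If a share q is wrongly failed and the true pass rate is π, the reported rate is π(1 − q). Assuming π = 80%:

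| q (assumed) | Reported rate |
|---|---|
| 10% | 0.80 × 0.90 = 72% |
| 25% | 0.80 × 0.75 = 60% |
| 50% | 0.80 × 0.50 = 40% |
| 75% | 0.80 × 0.25 = 20% |

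Seven wrongly failed patients of 45 (7/45 = 15.6 points) would move the estimate by about the plan's maximum margin of error. Late bookings scored as met, like E, push the other way.

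**6. Check of the remedy.** Starting the clock at surgery leaves A at 14 days and B at 18, both still above 10. A limit of postoperative day 20 (10 + 10) scores A, B and C as met.

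**The case against.** The best case for the plan is that the parenthesis exists to handle established patients and often does: patient D passes, so a pre-surgical consult alone causes no failure. No section makes pre-booking the postoperative visit a target, and Section 9.3 notes that the indication for adjuvant therapy is settled only after resection, so routine pre-booking cannot be presumed. The measure carries no test, and the go-forward rule in Section 9.4.3 rests on PORT delay and its racial disparity. Time to PORT is reported separately, so timely treatment would still be visible. All of this stands and limits the consequence. It does not repair the rule, which gives the wrong score whenever a patient is arranged early enough.

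Two stronger readings are tempting and are not supported:

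- A reader might infer that all three interval measures are mis-clocked. A referral placed before surgery meets Surgery to PORT Referral on the ordinary one-sided reading. RT Consult to Initiation is only ambiguous: it omits the word postoperative, but the measure before it specifies a postoperative consultation, and the 41-day sum points the same way. That an established patient might have no new referral to count is possible, but the documents do not say that it happens.
- A reader might infer a known ceiling on the reported proportion from the share of patients with established care. The documents give no such share, and the failing group is those referred or booked early, not everyone already seen.

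**Conclusion.** The point holds for one measure. RT Referral to Consult, as defined, tends to score a patient referred or booked before surgery as not met even when the postoperative visit and PORT are timely, and it can score a late-booked patient as met. This is a stated rule giving a wrong result, not just missing detail. It is a tendency rather than a certainty: the definition allows the consultation to take place in hospital, so a patient booked shortly before surgery and seen within the first days could still pass.

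The day counts follow from the definition. The effect on the reported proportion rests on an assumed share of early arrangements and an assumed true pass rate, so neither its size nor its net direction can be fixed from the documents. The measure is descriptive and secondary. The correction is worth making because it is cheap and removes a misclassification that works against early referral and booking.

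**What to change.** In Section 8.1, for referrals or appointments made before surgery, do not run the RT Referral to Consult clock from the pre-surgical date. Score the measure against a postoperative limit fixed in advance, for example postoperative evaluation by day 20, the sum of the plan's own referral and consult limits. Moving the start to the day of surgery is not enough on its own. State also whether a pre-surgical referral triggers this rule for an established patient whose visit is booked after surgery. If it does, patient E with a pre-surgical referral is correctly scored as not met (day 40 against day 20); if not, E still passes.

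Two accompanying clarifications:

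- In RT Consult to Initiation, say that the evaluation is the postoperative one.
- In Surgery to PORT Referral, say that a referral placed before surgery meets the measure, as does a postoperative RT appointment already in place for an established patient.

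The cost is a few words of definition plus abstraction of booking dates, including from radiation sites outside MUSC, which may take effort. Day 20 is a proposal that the plan does not contain, and it is somewhat uneven: a patient referred on day 2 must be seen by day 12, while a pre-booked patient has until day 20. The current definition can be reported alongside for comparability.

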
# Feasibility

NDURE Accrual is defined as the proportion of eligible patients who enroll in NDURE

NDURE Completion is defined as a participant completing the baseline assessment, at least two NDURE intervention sessions, and the final follow-up assessment

Navigation Session Completion is the number of NDURE navigation sessions completed by a participant

Navigator Caseload is the number of simultaneous cases (on-trial participants) being navigated by the NDURE navigator

Navigator Time Allocation (Direct) is the time (in minutes), that the NDURE navigator spends directly interacting with the patient to identify and address barriers to timely, equitable postoperative radiation therapy

Navigator Time Allocation (Indirect) is the time (in minutes), that the navigator spends generating and enacting each Barrier Reduction Plan that is not directly interacting with the patient

# Acceptability

Satisfaction with the Interpersonal Relationship with the Navigator Scale is, a validated, 9-item measure of the satisfaction of the interpersonal relationship with the patient navigator that has been used in prior studies of PN.

Satisfaction with Logistical Aspects of Navigation Scale is a validated, 26-item measure of the satisfaction of the logistical aspects of PN that has been used in prior studies of PN.

#### **Health Behavior Constructs**

Care Transition Measure-15 (CTM-15) is a validated, psychometrically sound 15-item, unidimensional measure of care transitions across the healthcare system that is consistent with the concept of patient-centeredness and useful from an organization perspective for the purpose of performance measurement and quality improvement. Higher scores reflect higher levers of care integration and coordination.

Communication & Attitudinal Self-Efficacy Scale (CASE)-Cancer is a validated, psychometrically sound 12-item scale that addresses three domains of self-efficacy in cancer care (understanding and participating in care, maintaining a positive attitude, and seeking and obtaining information). The CASE-Cancer scale has been used extensively in PN studies to measure perceived self-efficacy. Responses are on a 4-point Likert scale with higher scores indicating higher levels of self-efficacy.

Interpersonal Support Evaluation List-12 (ISEL-12) is a validated, 12-item assessment of three domains of interpersonal support that has been used to assess support in prior PN studies. Items are rated on a 4-point Likert scale with higher scores indicating more support.

Perceived Susceptibility Questionnaire is modified version of a validated 3-item perceived susceptibility subscale for mammography screening to assess perceived susceptibility for delays starting PORT after HNC surgery. Items are rated on a 5-point Likert scale with higher scores indicating higher perceived susceptibility.

Illness Perception Questionnaire-Revised (IPQ-R) consequences subscale (HNC modification). The IPQ-R consequences subscale is easily modifiable to asses disease-specific perceived severity. The IPQ-R is a validated assessment of a patient's self-representation of the health consequences of their illness. It is scored using a 5-point Likert scale with higher scores indicate higher perceived severity.

Perceived Barriers Questionnaire is a self-report measure of the presence/absence of pre-specified barriers to cancer care (yes/no). The questionnaire has been used extensively to assess perceived barriers in prior PN studies.

# Covariates

Behavioral Risk Factor Surveillance Survey (BRFSS) Demographics. The BRFSS is the nation's premier health-related survey that collects data about health-related risk behaviors from US residents. The demographic section from the BRFSS will be used (in-person) to ascertain participant sex, age, race, marital status, insurance, educational attainment, living situation, zipcode, phones for personal use, employment, and annual household income.

BRFSS Tobacco Use and Alcohol Consumption. The tobacco use and alcohol consumption sections of the BRFSS will be used (in-person) to characterize total cigarette exposure, current cigarette use, quit attempts, days of alcohol consumption, average drinks/day, frequency of  $\geq$  5 drinks, and maximum number of drinks.

Clinical and Oncologic Characteristics. Clinical characteristics will include comorbid medical conditions, and cancer history. Oncologic characteristics will include HNC tumor subsite, HNC tumor histology, p16/human papillomavirus (HPV) tumor status, American Joint Committee on Cancer TNM Class and overall stage grouping, type of ablative surgery, type of reconstruction, treatment dates, facility of planned adjuvant therapy, and adjuvant treatment type planned (adjuvant radiation or chemoradiation).

Barrier Load Survey will measure 1) the number of barriers identified in the BRP during NDURE; and 2) the type of barrier in our modified version of existing PN logs

Cultural Factor Survey is a validated, psychometrically sound questionnaire consists of three subscales assessing temporal orientation (5 items), collectivism (6 items), and religiosity (9 items). Prior PN studies have used these scales to measure cultural factors.

MD Anderson Symptom Inventory-Head Neck (MDASI-HN) is a validated, psychometrically sound, 28-item multisymptom patient-reported outcome measure for clinical and research use that assesses the severity of symptoms experienced by patients with cancer (including 9 HNC-specific symptoms), and the associated interference with daily living caused by these symptoms. Higher scores indicate more severe symptom/symptom interference.

# 9 STATISTICAL CONSIDERATIONS

# 9.1 STATISTICAL HYPOTHESES

• Primary Endpoint(s):

Because this is a pilot study generating preliminary data, our single-arm trial is not powered to detect a pre-specified improvement (i.e. reduction) in the rate of delayed PORT with NDURE. As such, the primary endpoint will be assessed via descriptive statistics. Hypotheses will be generated from the preliminary data for testing in future studies.

• Secondary Endpoint(s):

# Initiation of postoperative PORT > 6 weeks after surgery

We hypothesize that, compared to historical control data for patients undergoing surgery for HNC at MUSC followed by PORT between 2014-2016, patients who receive NDURE will have a decreased rate of PORT delays (initiation of PORT > 6 weeks after surgery).

Alternatively, our null hypothesis is that there will be no difference in the rate of PORT delay between patients who receive NDURE when compared to historical control data for patients undergoing surgery for HNC at MUSC followed by PORT between 2014-2016.

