# Initiation of postoperative PORT > 6 weeks after surgery

We hypothesize that, compared to historical control data for patients undergoing surgery for HNC followed by PORT in the National Cancer Database between 2006-2014, patients who receive NDURE will have a decreased rate of PORT delays (initiation of PORT > 6 weeks after surgery).

Alternatively, our null hypothesis is that there will be no difference in the rate of PORT delay between patients who receive NDURE when compared to historical control data for patients undergoing surgery for HNC followed by PORT in the National Cancer Database between 2006-2014.

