
Every effort will be made to minimize missing data and lost-to-follow-up participants. Participants will complete assessments at baseline and post intervention using an iPad-based REDCap collection method. The program coordinator will attempt to contact patients at least three times using a variety of methods of communication (e.g. text message, phone call, email, mail, etc) to complete outcome measures. This method resulted in 100% instrument completion in prior studies conducted by our team. Patients in the ITT population for whom the primary endpoint is not evaluable due to loss to follow-up will be considered NDURE failures, and their time to PORT will be treated as exceeding 6 weeks for the purposes of analysis (a very conservative approach for this single-arm, phase II pilot study. In the event that missing data occur for other endpoints, we will address them via standard multiple imputation procedures. In general, less than 10% missing data has little impact on study power and does not induce bias regardless of the missing data mechanism. If missing data is greater than 10%, it will be imputed using Markov Chain Monte Carlo (MCMC) methods. The data augmentation will be applied to Bayesian inference with missing data by repeating imputation step (i.e., simulating the missing values based on the observation) and step for exploring the posterior distribution based on the complete sample estimates obtained from the imputation step.

Our plan to accrue 45 patients (white, n=30 and AA, n=15) to the study over 13 months is highly feasible. Based on data from MUSC/HCC for 2018, it is expected that 125 patients/year will be eligible for the study, of whom 28 (22%) are expected to be AA and 97 (78%) are expected to be white. Based on the PI and study team's prior experience recruiting and enrolling for similar studies embedded into clinical care, we anticipate that 50% of eligible patients will accrue to this study. Based on this 50% accrual rate, over the course of 13 months, we would expect to accrue 68 patients (n=15 AAs; n=53 white). Thus, by conservative estimates with appropriate over-sampling of AAs, our overall accrual target (n=45) and for the AA racial subgroup (n=15) appear highly feasible in the allocated 13 month accrual period.

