#### 9.3 POPULATIONS FOR ANALYSES

Prior to studying the NDURE intervention in a phase II clinical trial, we will pre-test our intervention in n=3 patients to ensure proper implementation into clinical workflow. These patients will participate in the intervention and outcome assessment only for the purposes of pre-testing and assessing our implementation into clinical workflow but not for the purposes of analysis towards any of the study endpoints.

For the efficacy analysis, we will utilize a modified intention-to-treat (ITT) population. Participants will be part of the modified ITT population as defined by the following criteria:

- 1. Randomized to NDURE or Usual Care
- 2. Receipt of curative intent surgery at MUSC
- 3. Indication for PORT (with or without concurrent chemotherapy) per NCCN Guidelines based on the presence of at least one of the following adverse features on final pathologic evaluation: ENE, positive margin, pT3 or pT4 primary, N2 or N3 nodal disease, nodal disease in levels IV or V, PNI or LVI

As such, the modified ITT analytic population addresses the fact that eligibility, registration, randomization, and delivery of a portion of the intervention (NDURE or Usual Care) occur prior to definitive treatment of the HNSCC. However, the primary study objective (and endpoint) are defined and evaluable only for patients who undergo surgery for HNSCC and have an indication for adjuvant therapy (which can only be definitively known following surgical resection). As such, we expect that a predictable subset of patients will be enrolled in the study, based on meeting all inclusion, be randomized to NDURE or Usual Care, receive a portion of the intervention (NDURE Visit 1) and then subsequently develop a study exclusion criterion based on interval information that becomes available later in the clinical course that cannot be known at the time of study enrollment and registration, namely:

- failure to undergo curative intent surgery at MUSC (exclusion criteria #4)
- lack of indication for PORT (with or without chemotherapy) per NCCN Guidelines (exclusion criteria #5)

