As such, patients who meet study inclusion criteria but subsequently develop exclusion criteria #4 or #5 during the course of the study will be replaced since the primary endpoint is anchored to findings that occur after analysis of the pathologic specimen obtained during surgery. Patients in the modified ITT population for whom the primary endpoint is not evaluable due to loss to follow-up will be considered navigation failures, and their time to PORT will be treated as exceeding 6 weeks for the purposes of analysis.

We will also perform an efficacy analysis on the per-protocol analytic dataset, a subset of the modified ITT population who completed all 3 NDURE study sessions. These patients are judged to have complied with the protocol sufficiently to ensure that these data would be likely to represent the effects of the NDURE intervention according to the underlying scientific model.

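### As worded, the historical controls are patients who received PORT, while the NDURE set is patients with an indication for PORT and losses scored as delayed, so the Section 9.4.3 comparison uses unlike denominators.

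*Combined protocol and SAP*

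**What the plan says.** Section 9.1 names two comparators for the rate of PORT delay. The local one is "historical control data for patients undergoing surgery for HNC at MUSC followed by PORT between 2014-2016". The national one is "patients undergoing surgery for HNC followed by PORT in the National Cancer Database between 2006-2014". Both descriptions make receipt of PORT part of the definition.

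Section 9.3 defines the NDURE efficacy set differently: "For the efficacy analysis, we will utilize a modified intention-to-treat (ITT) population". Besides assignment and curative-intent surgery at MUSC, the criterion for entry is "Indication for PORT (with or without concurrent chemotherapy) per NCCN Guidelines based on the presence of at least one of the following adverse features", judged from the surgical specimen. Starting PORT is not required. Patients in this set who are lost to follow-up, so that the primary endpoint cannot be evaluated, "will be considered navigation failures, and their time to PORT will be treated as exceeding 6 weeks for the purposes of analysis". Section 9.2 gives the same rule and calls it "a very conservative approach for this single-arm, phase II pilot study".

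Section 9.4.3 compares the NDURE findings with both controls by Fisher's exact test. It adds a rule: if the upper 95% bound for NDURE is at or below the lower 95% bound for the control, further testing in a larger trial is taken to be warranted. The rule also covers the racial disparity in delay. The section asks for cautious interpretation because the data are not randomized. It does not mention the denominators.

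**The concern.** A historical patient who had an indication for PORT but died, declined or was lost before starting is, on the wording of Section 9.1, not in the control. The same kind of patient stays in the NDURE denominator and, if lost, counts as delayed. The difference between NDURE and history therefore contains a term that has nothing to do with navigation. It would remain with identical case mix, so the caveat about non-randomized data does not address it.

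The comparison is a stated secondary objective. Section 4.2 says that the design exists to give estimates relative to historical controls for planning a cluster-randomized trial, and the bound-separation rule is the plan's only numerical criterion for recommending that trial. The per-protocol set does not help: it requires three sessions, not a PORT start.

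**Working it through.** **Inputs from the documents**
- NDURE n = 45, of whom 15 are AA and 30 white (Section 4.1).
- Historical delay rate 56% (Sections 2.1 and 2.2). Its sample size and CI are not given, and no MUSC rate is given.
- On-treatment mortality below 5% (Section 5.5). This is the only loss-type rate given.

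**Assumptions**
- The fraction q of NDURE patients lost (or their number k).
- The lower confidence bound of the control.
- The true delay rate under NDURE.

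**1. The plan's own precision.** Half-width at p = 0.5 is 1.96 × √(0.25/n). For n = 45 this is 0.146 (stated 0.15), and for n = 15 it is 0.253 (stated 0.25). Both reproduce.

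**2. Shift in the overall rate with no true effect.** Let d = 0.56 among starters in both cohorts. With losses scored as delayed, the NDURE rate is q + (1 − q)d, so the shift is q(1 − d) = 0.44q.

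| q | Shift (points) | NDURE rate |
|---|---|---|
| 2% | +0.9 | 56.9% |
| 5% | +2.2 | 58.2% |
| 10% | +4.4 | 60.4% |

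Per patient the shift is 0.44/45 = 0.98 points. One, two, three and five losses give 57.0%, 58.0%, 58.9% and 60.9%.

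**3. Racial disparity.** With the same 56% among starters, one loss moves the AA rate by 0.44/15 = 2.9 points and the white rate by 0.44/30 = 1.5 points. One AA loss therefore widens the AA-minus-white difference by 2.9 points, and one white loss narrows it by 1.5. If both groups lose the same fraction q, the difference becomes (1 − q) times the difference among starters. The direction depends on who is lost.

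**4. Effect on the bound-separation rule.** Section 9.4.3 does not name the CI method, and exact intervals are used here. With an assumed historical lower bound of 0.55, the rule needs at most 17 of 45 delayed: the upper bound is 0.535 for 17 and 0.557 for 18. With k losses scored as delayed, the chance of passing is P(X ≤ 17 − k), where X is binomial with 45 − k patients. The second row uses a lower bound of 0.45, which allows at most 13 of 45.

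| Lower bound, true delay among starters | k=0 | k=1 | k=2 | k=3 | k=5 |
|---|---|---|---|---|---|
| 0.55, 35% | 71% | 64% | 56% | 48% | 31% |
| 0.45, 30% | 51% | 42% | 33% | 24% | 11% |

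**5. Patients known never to start.** The endpoint in Section 8.1 is defined by the interval to the start of radiation. The scoring rule in Sections 9.2 and 9.3 covers loss to follow-up only. A patient who is followed but refuses, dies or progresses before PORT has no stated score.

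**The case against.** The strongest objection is that the control denominators are read from a short phrase. The synopsis describes the NDURE population as having surgery at MUSC and then PORT, and Section 4.1 says much the same of the 45 patients, so the protocol also uses this wording loosely for its own cohort. How the cited sources treated non-starters cannot be seen from the documents. This stands and limits confidence. It does not remove the point, because Section 9.3 is the operative definition for NDURE and nothing in Section 9.4.3 aligns the two sides.

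Second, the loss rule is openly conservative and losses should be few. Section 5.5 puts contact at the scheduled sessions near 100%, and Section 6.1.1 has the navigator tracking barriers until PORT starts. With one or two losses, the shift of 1 to 2 points is small beside a half-width of about 15 points. This also stands for the point estimate. However, the shift is systematic, the CI does not reflect it, and the rule is a threshold.

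Third, a starters-only analysis conditions on an event that navigation may itself change. If NDURE brings hard-to-reach patients to a late start, that analysis penalizes it. This is why it should supplement the modified ITT comparison and not replace it.

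A reader might also infer that the mismatch could make NDURE look better than it is. That would require known non-starters to sit in the denominator and count as not delayed, and no section says so.

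**Conclusion.** On the protocol's wording the two sides of the historical comparison have different denominators. Under the only written scoring rule, the overall comparison is biased against NDURE by about 1 point per lost patient in 45. This rests on 56% delay among starters and on assumed loss rates, since the documents give none. The bias cannot create a false signal of benefit in the overall rate, but it can lower the estimate carried into the next trial and the chance of meeting the rule. For the racial disparity the direction is unknown. The score for known non-starters is a gap, not a demonstrated bias in either direction.

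Two stronger readings are not supported. The documents do not show that the control data sets actually exclude non-starters; they only describe them that way. Nor does missing the rule end development: Section 9.4.3 states when further testing is warranted and does not say what follows otherwise. The primary endpoint is descriptive and makes no historical comparison, and the stated precision is unaffected. This is an inexpensive improvement to a secondary comparison, held with moderate confidence.

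**What to change.** In Section 9.4.3:
- Keep the modified ITT rate as the primary descriptive estimate and keep its comparison with history.
- Beside each historical comparison, including the bound-separation rule, add a comparison restricted to NDURE patients who started PORT, labelled as conditional on starting.
- Report the number lost and the number who never started, by race, next to it.
- State how a patient known never to start PORT is scored in the modified ITT rate.

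Where MUSC records allow, define the local control instead by the Section 9.3 rule (curative-intent surgery at MUSC plus a listed adverse feature, whether or not PORT was given), with identical scoring of losses and non-starters. That would make the local comparison like for like without conditioning on a PORT start. In Section 9.1, state which denominator each control uses.

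The starters-only addition needs wording and no new data. Its drawback is that it conditions on a post-intervention event and must be interpreted so. Rebuilding the local control needs a new query of surgical records, and whether non-starters can be recovered from them is not known.
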